Parameter	Description/Definition
Sociodemographic characteristics	Age, sex, complimentary universal health care (CMU-c), aid for complementary health care (ACS) for elderly patients, department of patient's residence
Medical history and comorbidities	Identified algorithmically with hospital diagnoses, active long-term disease, drugs and medical procedures: Coronary arterial diseases (CAD), Dementia (Alzheimer dementia/vascular dementia/other dementia), Ischemic or hemorrhagic stroke (intracranial bleeding) Congestive Heart failure, Peripheral arterial disease, Other vascular diseases; Sleep disorders; Active cancer (within 6 months in the historical period) Age adjusted Charlson Cormordity Index (ACCI) adapted to the SNDS data (20) ; Frail patient identified by Claims-Based Fragility Index (CFI) adapted to the SNDS data (21) ; Malnutrition ; Morbid Obesity; Anemia; COPD Diabetes Patients at risk of falls identified by an algorithm adapted to SNDS data (22) ; Patients poly-medicated Patient with at least one nursing home entry available
Drug exposure	AF patients exposed to VKA, apixaban, rivaroxaban, dabigatran AF patients unexposed to OAC
Associated treatments	Beta-blockers, antihypertensives, antiplatelet drugs, other anticoagulants, Non-steroidal anti-inflammatory drugs (NSAIDs), oral corticoids, proton pump inhibitors, Selective serotonin reuptake inhibitor antidepressants (SSRIs), systemic azole antifungals, medical procedure of cardioversion, CYP P450 inhibitors, protease inhibitors
Left atrial appendage (LAA) occlusion	Medical procedure of treatment of thromboembolic risk in AF in alternative of OAC
Modified risk scores in AF	Thromboembolic risk: Modified CHA ₂ DS ₂ VASC identified by an algorithm adapted to SNDS data Hemorrhagic risk: Modified HAS-BLED identified by an algorithm adapted to SNDS data

Parameter	Description/Definition
Annual standardized incidence rate of AF	Ratio of number of newly diagnosed non valvular AF patients to the number of individuals in the French population per calendar year (N per 100,000 inhabitants) standardized on age using the 2019 French population structure and 2020 in sensitivity analyses.
Annual prevalence of AF	Ratio of number of diagnosed NVAF patients to the number of individuals in the French population (INSEE data) per calendar year (N per 100,000 inhabitants).

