Appendix 4 Identification of medical history and comorbidities

Disease	ICD-10 codes
Coronary arterial disease (CAD)	I21, I22, I24, I25
Sleep disorders	G47
Cancer	C00 to C80, D00 to D09, D37 to D48, Z510, Z511
Malnutrition	E43, E44, E46,
Morbid obesity (BMI>30)	E66
Hospitalisation for anemia	D50, D53
COPD	J44.9
Peripheral arterial disease	I70.0, I70.2, I70.9
Diabetes	E08, E10, E11, E13, E14
Congestive Heart failure	I50.2, I50.3, I50.4

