- Medical history and comorbidities (identified algorithmically with hospital diagnoses, active long-term disease, drugs and medical procedures): coronary arterial diseases (CAD), dementia, ischemic or hemorrhagic stroke, congestive Heart failure, peripheral arterial disease, other vascular diseases, sleep disorders, active cancer (within 6 months in the historical period), age adjusted Charlson Cormordity Index (ACCI) adapted to the SNDS data, frail patient identified by Claims-Based Fragility Index (CFI) adapted to the SNDS data, malnutrition, morbid Obesity, anemia, COPD, history of diabetes, patients at risk of falls identified by an algorithm adapted to SNDS data, patients poly-medicated, patient with at least one nursing home entry available;

	
 - Modified risk scores in AF: 1) thromboembolic risk: modified CHA2DS2VASC identified by an algorithm adapted to SNDS data; 2) hemorrhagic risk scores: modified HAS-BLED identified by an algorithm adapted to SNDS data; - Concomitant treatments: beta-blockers, antihypertensives, antiplatelet drugs, other anticoagulants, non-steroidal anti-inflammatory drugs (NSAIDs), oral corticoids, proton pump inhibitors, Selective serotonin reuptake inhibitor antidepressants (SSRIs), systemic azole antifungals, medical procedure of cardioversion, CYP P450 inhibitors, protease inhibitors, antiarrhythmics, glucose-lowering drugs, lipid-lowering drugs, digitalis glycosides, nitrates derivatives. - Annual standardized incidence rate and prevalence of AF, in exposed and unexposed to OAC, every year (2016-2020); - OAC treatment patterns: Line of treatment / regimen, number of lines of treatment (LOT), duration of treatment, time to next treatment; - Healthcare Resource use (HCRU) and associated costs: ambulatory care, hospital care (MCO), rehabilitation care facilities (SSR), Medications.

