8.1 Primary Objective

1. To estimate the incidence rate of stroke (ischemic or hemorrhagic), major bleeding and death in both non-valvular AF patients exposed to OAC (VKA or DOAC) and unexposed to OAC, overall and in the following subgroups of interest:
 - Elderly (≥ 80 years old)
 - Patients with CAD
 - Frail patients
 - Patients reported with active cancer
 - Patients reported with previous stroke

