Age ≥ 80 years old	
Binary variable (<80 years old / ≥ 80 years old)
 
Derived based on the date of birth attributed to the patient after cleaning the data extraction
 
Equals to:
 
 13. “<80 years old” if the absolute difference between the year of index date and the year of birth is strictly lower than 80 years old 14. “≥ 80 years old” if the absolute difference between the year of index date and the year of birth is upper than 80 years old 
See also Data Management Plan in section Error! Reference source not found.

History of coronary arterial disease (CAD)	
Binary variable (Yes / No)
 
Equals to “Yes” if the patient meets any criterion below on or in the 2 years prior to the index date:
 
 15. Is hospitalized with any diagnosis (i.e., main, related or associated diagnosis) of coronary arterial disease 
ICD-10 codes: I21.x, I22.x, I24.x, I25.x
 
OR
 
 – Is covered by the LTD status for coronary arterial disease at least one day 
ICD-10 codes: I21.x, I22.x, I24.x, I25.x
 
Equals to “No” in other cases

Claims-based Frailty Index (CFI) (for frail patients’ derivation)	
Continuous variable (between 0 and 1)
 
Claims-based frailty index (CFI) estimates a deficit-accumulation frailty index from a clinical assessment using International Classification of Diseases (ICD) diagnosis codes, Current Procedural Terminology (CPT) codes, and Healthcare Common Procedure Coding System (HCPCS) codes in the prior 2 years in administrative claims data.
 
See more details on calculation of CFI in Appendix 22

Frail patients	
Binary variable (Yes / No)
 
Equals to “Yes” if the Claims based Frailty Index (CFI) is upper or equal to 0.20
 
See Table I variable Claims based Frailty Index (CFI)

Active cancer	Binary variable (Yes / No)

Equals to “Yes” if the patient meets any criterion below in the 2 years before index date:
 
16. Is hospitalized with any discharge diagnosis (i.e., main, related or associated diagnosis) of active cancer
 
ICD-10 codes: C00.x to C80.x, D00.x to D09.x, D37.x to D48.x, Z51.0, Z51.1
 
OR
 
 – Is covered by the LTD status for active cancer at least one day 
ICD-10 codes: C00.x to C80.x, D00.x to D09.x, D37.x to D48.x, Z51.0, Z51.1
 
Equals to “No” in other cases
	

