HIV-AIDS (for ACCI derivation)	
Binary variable (Yes / No)
 
Derived based on (24)
 
Equals to "Yes" if the patient meets any criterion below on or in the 2 years prior to the index date:
 
 – Is hospitalized at least once with any diagnosis (i.e., main, related or associated diagnosis) of HIV-AIDS 
ICD-10 codes : B20.x, B21.x, B22.x, B24.x, F02.4, Z21.x
 
OR
 
 – Is covered by the LTD status for HIV-AIDS at least one day 
ICD-10 codes : B20.x, B21.x, B22.x, B24.x, F02.4
 
OR
 
 – Has reimbursements for at least 3 dispensations at pharmacy of any anti-retroviral drugs specific to the treatment of HIV-AIDS 
ATC codes: 05AF01, J05AF02, J05AF03, J05AF04, J05AF06, J05AF13, J05AG01, J05AG03, J05AG04, J05AG05, J05AR01, J05AR02, J05AR04, J05AE01, J05AE02, J05AE03, J05AE04, J05AE05, J05AE07, J05AE08, J05AE09, J05AE10, J05AR10, J05AR06, J05AR08, J05AR09, J05AR13, J05AR18, J05AR19, J05AX07, J05AX08, J05AX09, J05AX12
 
OR
 
 – Has at least one reimbursement for a biological test specific to the treatment of HIV-AIDS 
NABM codes: 0805, 0806, 1691, 4117, 4122
 
Equals to "No" in other cases

Any tumor (including lymphoma and leukemia except for malignant neoplasm of skin) (for ACCI derivation)	
Binary variable (Yes / No)
 
Equals to "Yes" if the patient meets any criterion below on or in the 2 years prior to the index date:
 
 – Is hospitalized at least once with any discharge diagnosis (i.e., main, related or associated diagnosis) of any tumor (including lymphoma and leukemia except for malignant neoplasm of skin) 
ICD-10 codes : C00-C26 ;C30-C34 ;C37-C41 ;C43 ; C45-C58 ; C60-C76 ;C81-C85 ;C88 ; C90-C97
 
OR

	
 – Is covered by the LTD status for any tumor (including lymphoma and leukemia except for malignant neoplasm of skin) at least one day 
ICD-10 codes : C00-C26 ; C30-C34 ; C37-C41 ; C43 ; C45-C58 ; C60-C76 ; C81-C85 ; C88 ; C90-C97
 
Equals to “No” in other cases

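### SAP Table V derives the primary-objective active-cancer subgroup over 2 years, while the protocol and the SAP abstract say 6 months; separately, neither document lists any C81-C97 code.

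*SAP*

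**What the plan says.** SAP section 8.1 names "Patients reported with active cancer" among the five subgroups of the primary objective. It gives no time window there, and neither do the subpopulation lists in protocol section 3.2.2 and SAP section 9.2.3.4.

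The window is stated in three places:

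- Protocol Appendix 1, Table A1.5: "Active cancer (within 6 months in the historical period".
- SAP section 4 (abstract, variables): "active cancer (within 6 months in the historical period".
- SAP section 9.4.1, Table V, which holds the derivation: the patient "meets any criterion below in the 2 years before index date". The criteria are a hospital stay with a listed code in any diagnosis position, or "Is covered by the LTD status for active cancer at least one day".

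SAP Table XIII, on comorbidities, only points back to Table V for active cancer.

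The Table V code list is "C00.x to C80.x, D00.x to D09.x, D37.x to D48.x, Z51.0, Z51.1". Protocol Appendix 4 gives "C00 to C80, D00 to D09, D37 to D48, Z510, Z511" for cancer. The Any tumor component of the age-adjusted Charlson index (ACCI) in SAP Table VI says that it covers lymphoma and leukaemia, and its list ends "C60-C76 ;C81-C85 ;C88 ; C90-C97".

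**The concern.** The SAP contradicts itself and the protocol on who belongs to a primary-objective subgroup. The version that will be programmed is the one that differs from the stated definition. Table V uses the same look-back length for history of coronary disease and for previous stroke, so a variable labelled active is built like a history variable.

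At stake is what the active-cancer version of Table A2 means. A reader of the protocol or the abstract would take its rates to describe patients with cancer evidence in the preceding half year. The table would in fact describe anyone with a cancer stay, or one day of cancer LTD cover, in two years. The same variable stratifies the annual incidence and prevalence tables (A12 and A13) and enters the clustering.

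The second matter is scope. The SAP counts lymphoma and leukaemia as cancer when it scores comorbidity, but lists none of their C81-C97 codes when it defines this subgroup, and gives no reason.

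**Working it through.** The plan gives no size, event count or rate for this subgroup, so there is no figure to reproduce. The check compares the definitions.

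**Window**

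1. Stated window: 6 months (protocol Table A1.5 and SAP abstract), read as the 6 months before the index date.
2. Operative window: 2 years = 24 months (SAP Table V).
3. Ratio: 24 / 6 = 4.
4. Part of the operative window outside the stated one: 24 − 6 = 18 months, and 18 / 24 = 75%. This is a share of the window, not of patients.
5. Is the 6-month limit applied elsewhere? Table XIII refers back to Table V. The amendments table in SAP section 5 records none. None of the sensitivity analyses in SAP section 9.7.6 varies this window. So the limit is not applied anywhere.
6. Is a 2-year look-back simply the SAP's rule throughout? No. The recent bleeding-ulcer item among the contraindications in Table XII is limited to 6 months before index, so the SAP writes a shorter window where it wants one.

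**Effect on the rates**

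Let p be the share of the Table V subgroup's person-time that comes from patients whose only cancer evidence is 6 to 24 months old. Let λ_old be their event rate and λ_rec the rate in patients with evidence inside 6 months. Then

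λ_TableV = (1 − p) × λ_rec + p × λ_old,

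so λ_TableV − λ_rec = p × (λ_old − λ_rec).

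The documents give neither p nor the two rates, so neither the size nor the sign of the difference can be computed.

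**Codes, at three-character level**

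| List | C81-C97 categories listed (of 97 − 81 + 1 = 17) |
|---|---|
| SAP Table V, active cancer | 0 |
| Protocol Appendix 4, cancer | 0 |
| SAP Table VI, Any tumor | 5 (C81-C85) + 1 (C88) + 8 (C90-C97) = 14 |

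Table V and protocol Appendix 4 have identical lists: C00-C80, D00-D09, D37-D48, Z51.0 and Z51.1. A patient whose cancer is coded only in C81-C97 can therefore enter the subgroup only through a stay coded Z51.0 or Z51.1. Those codes carry no tumour-site restriction, and protocol Appendix 1 gives chemotherapy sessions as its example of Z-codes.

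**The case against.** The best defence on the window is that the protocol's 6 months sits in a table titled as indicative (section 3.5.1 describes it the same way), while the objectives and subpopulation sections set no window. On that view Table V is the detailed specification and takes precedence. This stands in part: the documents do not prove that 6 months is the intended rule. It does not remove the conflict, because the SAP's own abstract repeats the 6 months and no text explains the longer window.

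The reach is also limited. Active cancer is one of five descriptive rate subgroups and is not itself a listed covariate in the Cox models (SAP Table XV and section 9.7.4.2). The overall primary rates do not depend on it.

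A reader might infer four stronger things that the documents do not support:

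- That the SAP dropped codes which the protocol had. It did not. Protocol Appendix 4 carries the same list, so the C81-C97 gap belongs to both documents.
- That every haematological cancer is missed. Stays coded Z51.0 or Z51.1 can still bring some of these patients in.
- That the longer window lowers the rates. This is plausible, most of all for death, but nothing in the documents shows it for any of the three outcomes.
- That including D00-D09 and D37-D48, which the Any tumor list leaves out, is an error. Both documents list these codes for cancer, and a scored comorbidity item need not match a subgroup definition.

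**Conclusion.** The window contradiction is confirmed, and it alone makes the Table V subgroup differ from the one stated in the protocol and the SAP abstract. The window is 4 times as long, and patients whose only evidence is 6 to 24 months old would be counted as having active cancer. This rests on reading the 6-month phrase as the 6 months before index, which is its natural sense. The size and direction of the effect on the rates are unknown.

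The code gap is a separate and weaker matter: an unexplained omission shared by both documents and inconsistent with the SAP's own tumour variable. It is not a departure of the SAP from the protocol. Both points should be settled before the subgroup is programmed.

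**What to change.** 1. In SAP Table V, apply the stated 6-month window before index to the hospital codes, including Z51.0 and Z51.1.
2. State how the LTD route is limited. Shortening the window is not enough: under the one-day rule, LTD cover that began long ago and is still open at index would bring past cancer back in.
3. Keep the 2-year version, if wanted, as a separate history-of-cancer variable or as a sensitivity analysis.
4. If 2 years is what is intended, correct protocol Table A1.5 and the SAP abstract instead, justify the choice, and relabel the subgroup so that it is not called active.
5. Decide whether haematological cancers belong. If they do, add C81-C97 to both SAP Table V and protocol Appendix 4, because changing only one would create a new mismatch. If they do not, say so in the definition and in the table footnotes.

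The cost is one row in Table V, one matching line in the protocol appendix if codes are added, and a smaller subgroup from the shorter window.

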Appendix 5 Identification of treatments and left atrial appendage (LAA) occlusion

Drug- treatments	ATC or CCAM code
Antivitamin K	B01AA
apixaban	B01AF02
rivaroxaban	B01AF01
dabigatran	B01AE07
Selective serotonin reuptake inhibitor antidepressants (SSRIs)	N06AB
Antiarrhythmics	C01BA, C01BB, C01BC, C01BD, C01BG
Non-steroidal anti-inflammatory drugs (NSAIDs)	M01A;
CYP 3A4 cyt P450 inhibitors	B01AC24, C05AE03, C09BB10, C01BD01, J01FA excepté J01FA02
Proton pump inhibitors	A02BC
Systemic azole antifungals	J02AB et J02AC
Anti-platelet agents	B01AC
Medical procedure of cardioversion	DERP004, DERP003
Other anticoagulants	B01AB, B01AE, B01AF, B01AX
Antihypertensives	ATC: C02, C03, C07, C08, C09 (excluding : C02KX01 (not available in France), C03BA08 (not available for outpatient), C03CA01, C07AA07, C07AA12 (not available in France), C07AG02
glucose-lowering drugs	A10BA Metformin, A10BH DPP-IV inhibitors, A10BJ GLP- 1 receptor agonists, A10BX Glinide, A10BF Alpha Glucosidase inhibitors, A10BB Sulfonylurea and the combinations A10BD07, 08, 10 DPP-IV + Metformin and A10BD02 Sulfonylurea + Metformin and A10A insulins
lipid-lowering drugs	Statins: C10AA, C10BA, C10BX; fibrates: C10AB; omega 3 C10AX06; Monoclonal anti-PCSK-9C10AX13 and C10AX14
Beta-blockers	C07A, C07B, C07C, C07D, C07E, C07F
Antivirals, protease inhibitors	J05AE
CCAM code	LAA occlusion
DASF074	Non-English text

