Previous stroke	
Binary variable (Yes / No)
 
Equals to “Yes” if the patient meets any criterion below on or in the 2 years prior to the index date:
 
17. Is hospitalized at least once with any discharge diagnosis (i.e., main, related or associated diagnosis) of stroke (ischemic or haemorrhagic)
 
ICD-10 codes: I60.x, I61.x, I62.9, I63.x, I64.x, G45.x, G46.x, G81.x, S06.4, S06.5, S06.6
 
OR
 
 – Is covered by the LTD status for stroke (ischemic or haemorrhagic) at least one day 
ICD-10 codes: I60.x, I61.x, I62.9, I63.x, I64.x, G45.x, G46.x, G81.x, S06.4, S06.5, S06.6
 
Equals to “No” in other cases

Moreover, all the variables used to define stratification groups will be derived for each patient selected in the study population ([Table VII](#)).

Table VI. Derived variables for the selection of the population – Stratifications

Variable	Definition
Age groups	Categorical variable (<80, 80-90, >90 years old) See Table III
Heart failure history (for Modified CHAD ₂ DS ₂ VASC score strata derivation)	Binary variable (Yes / No) Derived based on (24)

Equals to "Yes" if the patient meets any criterion below on or in the 2 years prior to the index date:

- Is hospitalized at least once with any diagnosis (i.e., main, related or associated diagnosis) of cardiac failure

ICD-10 codes: I50.x, I11.0, I13.0, I13.2, I13.9

OR

- Is covered by the LTD status for cardiac failure at least one day

ICD-10 codes: I50.x, I11.0, I13.0, I13.2, I13.9

Equals to "No" in other cases

Hypertension history (for Modified CHAD ₂ DS ₂ VASC score strata derivation)	Binary variable (Yes / No) Derived based on (24) Equals to "Yes" if the patient meets any criterion below on or in the 2 years prior to the specified date:

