	
 - Is hospitalized with any diagnosis (i.e., main, related or associated diagnosis) of hypertension 
ICD-10 codes: I10.x, I11.x, I12.x, I13.x, I15.x, I67.4
 
OR
 
 - Is covered by the LTD status hypertension at least one day 
ICD-10 codes: I10.x, I11.x, I12.x, I13.x, I15.x, I67.4
 
OR
 
 - Has reimbursements for at least 3 dispensations at pharmacy of any antihypertensive drug 
ATC codes: C02AB02, C02AC01, C02AC02, C02AC05, C02AC06, C02CA01, C02CA02, C02CA06, C02DC01, C02LA01, C03AA01, C03AA03, C03BA04, C03BA10, C03BA11, C03BX03, C03CA01, C03CA02, C03CA03, C03DA01, C03DA02, C03DA04, C03DB01, C03EA, C03EA01, C03EA04, C03EB01, C07AA02, C07AA03, C07AA05, C07AA06, C07AA07, C07AA12, C07AA15, C07AA16, C07AA23, C07AB02, C07AB03, C07AB04, C07AB05, C07AB07, C07AB08, C07AB12, C07AG01, C07AG02, C07BA02, C07BB02, C07BB03, C07BB07, C07BB12, C07CA03, C07DA06, C07FB02, C07FB03, C08CA01, C08CA02, C08CA03, C08CA04, C08CA05, C08CA06, C08CA08, C08CA09, C08CA11, C08CA13, C08CX01, C08DA01, C08DB01, C08EA02, C09AA01, C09AA02, C09AA03, C09AA04, C09AA05, C09AA06, C09AA07, C09AA08, C09AA09, C09AA10, C09AA13, C09AA15,

	C09AA16, C09BA01, C09BA02, C09BA03, C09BA04, C09BA05, C09BA06, C09BA07, C09BA09, C09BA15, C09BB02, C09BB04, C09BB10, C09CA01, C09CA02, C09CA03, C09CA04, C09CA06, C09CA07, C09CA08, C09DA01, C09DA02, C09DA03, C09DA04, C09DA06, C09DA07, C09DA08, C09DB01, C09DB02, C09DB04, C09XA02, C09XA52, C10BX03
	OR

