Previous Stroke (for Modified CHAD₂DS₂VASC score strata derivation)	Binary variable (Yes / No) See Table V
Previous Transient Ischemic Attack (TIA) (for Modified CHAD₂DS₂VASC score strata derivation)	Binary variable (Yes / No) Equals to "Yes" if the patient is hospitalized at least once with any discharge diagnosis (i.e., main, related or associated diagnosis) of TIA, on or in the 2 years prior to the index date ICD-10 codes: G45 Equals to "No" in other cases
Previous systemic arterial embolism (TE)	Binary variable (Yes / No)

(for Modified CHAD ₂ DS ₂ VASC score strata derivation)	
Equals to “Yes” if the patient is hospitalized at least once with any discharge diagnosis (i.e., main, related or associated diagnosis) of TE, on or in the 2 years prior to the index date
 
ICD-10 codes: I74, N28, D73.5, K76.3

Previous Stroke, TIA, or TE (for Modified CHAD ₂ DS ₂ VASC score strata derivation)	
Binary variable (Yes / No)
 
Equals to “Yes” if the variable Previous stroke = “Yes” (see Table V) or the variable Previous Transient Ischemic Attack (TIA) = “Yes” or the variable Previous Thromboembolism (TE) = “Yes”
 
Equals to “No” in other cases

Myocardial infarction history (for Modified CHAD ₂ DS ₂ VASC score strata derivation)	
Binary variable (Yes / No)
 
Derived based on (20,23)
 
Equals to “Yes” if the patient meets any criterion below on or in the 2 years prior to the index date:
 
 - Is hospitalized at least once with any diagnosis (i.e., main, related or associated diagnosis) of myocardial infarction 
ICD-10 codes: I21.x, I22.x, I25.2, I25.5
 
OR
 
 - Is covered by the LTD status for myocardial infarction history at least one day 
ICD-10 codes: I21.x, I22.x, I23.x
 
Equals to “No” in other cases.

Peripheral artery disease (PAD) history (for Modified CHAD ₂ DS ₂ VASC score strata derivation)	
Binary variable (Yes / No)
 
Equals to “Yes” if the patient is hospitalized at least once with any diagnosis (i.e., main, related or associated diagnosis) of peripheral artery disease on or in the 2 years prior to the index date
 
ICD-10 codes: I70-I74, I771
 
Equals to “No” in other cases

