Bleeding history or predisposition (for HAS-BLED score derivation)	
Binary variable (Yes / No)
 
Equals to “Yes” if the patient is hospitalized with hospital-discharge summary with primary diagnosis of bleeding on or in the 2 years prior to the index date:
 
ICD-10 codes: D62, D683, D698, D699, H113, H313, H356, H431, H450, H922, I230, I312, I600-I616, I618-I621, I629, I850, I983, J942, K250, K252, K254, K256, K262, K264, K270, K272, K274, K276, K280, K282, K284, K286, K661, K920, K921, K922, M250, N020-N029, N421, N920, N921, N923, N924, N938, N939, N950, R040, R041, R042, R048, R049, R31, R58, S064, S065, S066, S260, S271, T792
 
Equals to “No” in other cases

Labile international normalized ratio (INR) (for HAS-BLED score derivation)	
Binary variable (Yes / No)
 
Not applicable to SNDS data (INR results are not captured in SNDS databases).

Elderly (for HAS-BLED score derivation)	
Binary variable (≤ 65 years old / > 65 years old)

Drugs predisposing to bleeding or alcohol concomitantly (for HAS-BLED score derivation)	
Binary variable (Yes / No)
 
Variable Drugs equals to “Yes” if the patient has at least one drug dispensation for antiplatelet agents (acetylsalicylic acid: B01AC06 ATC code, clopidogrel: B01AC04 ATC code) or NSAIDs (M01A ATC code) in the 4 months before the index date.
 
OR

	
Variable Alcohol equals to “Yes” if the patient is hospitalized with any discharge diagnosis (i.e., main, related or associated diagnosis) of all causes related to alcohol on or in the 2 years prior to the index date:
 
ICD-10 codes : E244, E512, F10, G312, G621, G721, I426, K292, K70, K860, R780, T51, X45, X65, Y15, Y90, Y91, Y573, Z502, Z714, Z721.
 
Equals to “No” in other cases

HAS-BLED score	
Continuous variable (between 1 and 9)
 
Derived based on (19)
 
Equals to sum of:
 
 ○ 1 point if the variable Hypertension equals to “Yes” ○ 1 or 2 points if the variable Abnormal renal and liver function equals to “Yes” (1 point each) ○ 1 point if the variable Stroke equals to “Yes” ○ 1 point if the variable Bleeding equals to “Yes” ○ 1 point if the variable Labile INRs equals to “Yes” ○ 1 point if the variable Elderly equals to “>65 years old” ○ 1 or 2 points if the variable Drugs or alcohol equals to “Yes” (1 point each)

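### Code lists behind CHA2DS2-VASc and HAS-BLED are inconsistent: the hypertension and N28 rules can raise a stratum, double-counted I74 changes only the score, and missing bleeding codes lower HAS-BLED

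*SAP*

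**What the plan says.** **Hypertension.** SAP 9.4.1, Table VI sets hypertension history to Yes through a hospital diagnosis, a long-term-disease entry or drugs. The main drug route reads "Has reimbursements for at least 3 dispensations at pharmacy of any antihypertensive drug"; a second route accepts two dispensings if one is a large pack. The drug list for both routes contains "C07AA06, C07AA07, C07AA12, C07AA15", "C03BX03, C03CA01, C03CA02" and "C07AG01, C07AG02, C07BA02". The look-back runs "on or in the 2 years prior to the specified date", and that date is not defined; neighbouring variables use the index date. Protocol Appendix 5 lists among the exclusions from its antihypertensive class "C03CA01, C07AA07, C07AA12 (not available in France), C07AG02". SAP Tables III and XIV define antihypertensives from C02, C03, C08 and C09, without C03CA01, and treat C07 separately as beta-blockers.

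**Embolism and peripheral artery disease.** The Table VI list for previous systemic arterial embolism is "I74, N28, D73.5, K76.3". The peripheral artery disease list for the same score spans I70 to I74 plus I77.1.

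**HAS-BLED.** SAP 9.4.3.1, Table XII reuses the Table VI hypertension variable. Its bleeding list contains the run "K250, K252, K254, K256, K262, K264, K270", so K26 appears only as K26.2 and K26.4. K22.6, K29.0 and K62.5 are also absent.

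**Use.** The modified CHA2DS2-VASc strata split the primary rates (Tables XXI and A2), and the High stratum defines the population of the second set of Cox models (SAP 9.7.4.2, Table A11). Table XV lists both scores as confounders.

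**The concern.** The same dispensing is not an antihypertensive in one table and is evidence of hypertension in another. The same embolism list is specific for two organs and open-ended for a third. One code earns points under two headings of the same score. One bleeding list leaves gaps that its own pattern and the SAP's other bleeding lists do not share.

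A single extra point can matter because the strata are narrow: Low, Moderate and High correspond to 0, 1 and 2 or more points beyond the sex point. A misplaced hypertension or embolism flag can therefore take a patient out of the Low or Moderate rates of Table A2 and into the High population of Table A11.

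**Working it through.** The plan gives no figure to reproduce here. The check is a code-list comparison plus re-adding the scores.

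**Inputs (SAP Table VI).** S = heart failure (1) + hypertension (1) + age (1 if 65-74, 2 if 75 or over) + diabetes (1) + stroke/TIA/embolism (2) + vascular disease (1) + female (1). Stratum by S minus the sex point: 0 Low, 1 Moderate, 2 or more High.

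**Step 1: drug codes.** Protocol Appendix 5 excludes six codes: C02KX01, C03BA08, C03CA01, C07AA07, C07AA12 and C07AG02. The last four are in the Table VI hypertension list. That list holds 27 C07 codes; Tables III and XIV place none under antihypertensives.

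**Step 2: single patients under 65, no other qualifying code or drug.**

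| Patient | Without the disputed code | With it |
|---|---|---|
| Man, heart failure, three C03CA01 dispensings | 1, Moderate | 1 + 1 = 2, High |
| Man, no risk factor, three C07AA07 dispensings | 0, Low | 1, Moderate |
| Man, one N28 code | 0, Low | 2, High |
| Woman, one N28 code | 1, Low | 1 + 2 = 3, High |
| Man, one I74 code (counted once, then twice) | 2, High | 2 + 1 = 3, High |
| Woman, one I74 code (counted once, then twice) | 3, High | 4, High |

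**Step 3: all component profiles.** There are 2 × 2 × 3 × 2 × 2 × 2 × 2 = 192 combinations of heart failure, hypertension, age band, diabetes, embolism group, vascular disease and sex. These are profiles, not patients.

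- *Hypertension switched on (96 profiles).* Zero non-sex points: 1 × 2 sexes = 2, Low to Moderate. One non-sex point (heart failure, age 65-74, diabetes or vascular disease): 4 × 2 = 8, Moderate to High. The other 86 stay High.
- *N28 embolism flag switched on (96 profiles).* Zero non-sex points: 2, Low to High. One non-sex point (the same four or hypertension): 5 × 2 = 10, Moderate to High. The other 84 stay High.
- *I74 also counted as vascular disease (48 profiles with embolism, without vascular disease).* All 48 are High before and after. The Table XV category (0, 1, 2, 3, 4, 5 or more) changes only where the score starts at 4 or less, that is, where the remaining points sum to 2 or less: 11 profiles under 65, 5 at 65-74 and 1 at 75 or over, so 17 of 48.

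**Step 4: HAS-BLED.** For K25, K27 and K28 the bleeding list has all four of the .0, .2, .4 and .6 codes; for K26 it has two. K26.0, K26.6, K22.6, K29.0 and K62.5 are all major bleeding in Table VIII and in the Table VI bleeding history. A patient whose only bleeding admission has K26.0 as primary diagnosis gets 0 bleeding points; with K25.0 the same patient gets 1. Neither I74 nor N28 enters HAS-BLED.

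**The case against.** The best defence is that no protocol definition of hypertension is breached. Appendix 5 defines a treatment class; for the scores the protocol says only that algorithms adapted to the SNDS will be used. The SAP derives hypertension history from its reference 24, the national health insurer's disease-mapping method, whose list is not in the documents. This stands: the drug-code item is an inconsistency to reconcile or justify, not a proven breach.

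The reach of the drug codes is also limited. They matter only for patients with no hypertension stay or long-term-disease entry and too few dispensings of the other listed drugs. If the undefined date is the index date, which lies at most 30 days after inclusion, drugs started at AF diagnosis will often fall short of three dispensings. Protocol Appendix 5 marks C07AA12 as not available in France, so it should add little. Removing C07AA07, C07AA12 and C07AG02 leaves 24 of the 27 C07 codes, so Table VI would agree with Appendix 5 but still differ from Tables III and XIV.

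The HAS-BLED bleeding variable is a different construct: it covers predisposition, uses the primary diagnosis only and holds codes absent from Table VIII. Adding five codes will not make the two lists identical. The gap within K26 is nevertheless hard to explain as intended.

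Covariate use is not fully settled: Table XV lists both scores, but the adjustment footnotes of Tables A10 and A11 name neither.

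**Conclusion.** The code lists need correction or justification. The hypertension and N28 items carry the weight, because they can move a patient up a stratum and so change the Table A2 strata and the Table A11 population. The I74 and bleeding-list items are secondary and affect score values only.

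Three stronger readings are not supported:

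- A reader might infer that all four defects push low-risk patients upward. The I74 double count moves none, and the bleeding omissions lower HAS-BLED.
- A reader might infer that the main result is biased. The overall primary rates and the five named subgroups do not use these scores. Nor do the documents print drug indications or link the disputed codes to the choice of anticoagulant.
- A reader might attach a patient count. The documents give neither the share of the cohort that is Low or Moderate nor the share carrying these codes, so no count can be derived.

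The conclusion assumes that the lists are programmed as written. The documents do not print the ICD-10 subcategory labels, so the N28 item rests on the contrast with D73.5 and K76.3 in the same list.

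**What to change.** In SAP Table VI:

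- Remove C03CA01, C07AA07, C07AA12 and C07AG02 from both hypertension drug routes so that they agree with protocol Appendix 5, or state that reference 24 requires them and why the difference is accepted.
- Anchor the hypertension look-back to the index date.
- Restrict N28 to N28.0 in the embolism list, after confirming against ICD-10 that this is the intended subcategory.
- Drop I74 from the peripheral artery disease list used for the score, so that it counts once, as embolism.

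In SAP Table XII, add K26.0, K26.6, K22.6, K29.0 and K62.5 to the HAS-BLED bleeding list.

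In SAP Table III, do not edit N28 by analogy. There it feeds a published model applied at a cut-off chosen for 95% specificity, and changing a predictor could invalidate that cut-off. Check it against the published algorithm and change it only if it is a transcription error.

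The adjustment footnotes of Tables A10 and A11 should also be aligned with Table XV, so that it is clear whether the scores are in the models.

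The cost is a set of code-list edits before programming, plus a look-up in two cited sources. No new data are needed.
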